20 JUN 2019

STUDY PROTOCOL

PASS Information

Title	Prospective controlled cohort study on the safety of a monophasic oral contraceptive containing nomegestrol acetate (2.5mg) and 17β-estradiol (1.5mg)
Protocol version identifier	V04-00
Date of last version of protocol	05 February 2014
EU PAS register number	EUPAS2196
Active substance	Pharmacotherapeutic group: Sex hormones and modulators of the genital system, progestogens and estrogens, fixed combinations, ATC code: G03AA14 Active substances: nomegestrol acetate and estradiol (as hemihydrate)
Medicinal product	Zoely 2.5 mg/1.5 mg film-coated tablets
Product reference	Zoely: EMEA/H/C/001213
Procedure number	Not available
Marketing authorisation holder(s)	Theramex Ireland Limited
	[name],
	[name],
	Dublin 1
	[name]
	Ireland
Joint PASS	No
Research question and objectives	Primary objective: characterization and comparison of the risks of the use of NOMAC- E2 with COC _{LNG} . Main clinical outcomes of interest: venous thromboembolism, specifically deep venous thrombosis of the lower extremities and pulmonary embolism.
Country(-ies) of study	Australia, Austria, Colombia, France, Germany, Hungary, Italy, Mexico, Poland, Russia, and Spain, Sweden

Author	[name], PhD Principal Investigator [name]
	[name]
	Germany
	Phone:

PASS Information (continued)

Marketing authorisation holder(s)

Marketing authorisation holder(s)	Theramex Ireland Limited [name], [name], Dublin 1 [name] Ireland
Contact person	Merck & Co Inc [name] [name] United States Telephone - Office:

1 Table of Contents

1	Table of Contents 3			
2	List of Abbreviations			
3	Responsible Parties			
4	Absti	ract	8	
5	Ame	ndments and undates		
6	Mile	stones	38	
7	Datio	onals and background	20	
/ 0		onale and background		
0	Rese	arch question and objectives		
9	Kese	earch methods		
	9.1	Study design		
	9.2	Setting		

Annex 1. List of stand-alone documents	
Annex 2. ENCePP checklist for study protocols	
Annex 3. Additional information	

PASS – Safety of nomegestrol/estradiol: Study Protocol Version 4.0 20 JUN 2019

2 List of Abbreviations

Abbreviation	Definition
ADB	Administrative Database
AE	Adverse Event
AMI	Acute Myocardial Infarction
АТ	As Treated
ATC	Anatomical Therapeutic Chemical Classification System
ATE	Arterial Thromboembolism
BMI	Body Mass Index
CHMP	Committee for Medical Products for Human Use
COC	Combined Oral Contraceptive
	Levonorgestrel-containing COC
СТ	Computer Tomography
CVA	Cerebrovascular Accidents
DIMDI	German Institute for Medical Documentation and Information
DVT	Deep Venous Thrombosis
ECG	Electrocardiogram
EMA	European Medicines Agency
ENCePP	European Network of Centres for Pharmacoepidemiology and Pharmacovigilance
EURAS	European Active Surveillance (study)
GEP	Good Epidemiological Practices
GPP	Good Pharmacoepidemiology Practices
GXP	Good Practice Guidelines
HR	Hazard Ratio
IBD	Inflammatory Bowel Disease
ICD-10	International Classification of Diseases, 10th revision

Protocol/Amendmen	t No.: P08291 Amendment 1			
PASS – Safety of nomegestrol/estradiol: Study Protocol Version 4.0 20 JUN 2019				
ICMJE	International Committee on Medical Journal Editors			
INAS	International Active Surveillance Study			
ITT	Intention To Treat			
LNG	Levonorgestrel			
MRT	Magnetic Resonance Tomography			
NOMAC-E2	Nomegestrol Acetate and Estradiol			
OC	Oral Contraceptive			
OPS	Operations and Procedures Classification System (acronym for the German term 'Operationen- und Prozedurenschlüssel')			
PE	Pulmonary Embolism			
PIP	Pediatric Investigation Plan			
PMDD	Premenstrual Dysphoric Disorder			
PMS	Premenstrual Syndrome			
PRAC	Pharmacovigilance Risk Assessment Committee			
PQC	Product Quality Complaint			
SAE	Serious Adverse Event			
SDB	Study Database			
SMAC	Safety Monitoring and Advisory Council			
TASC	Transatlantic Active Surveillance on Cardiovascular Safety of NuvaRing			
VTE	Venous Thromboembolism			
WHO	World Health Organization			
WY	Woman-years			
ZEG	Berlin Center for Epidemiology & Health Research (acronym for the German term 'Zentrum für Epidemiologie & Gesundheitsforschung Berlin')			

PASS – Safety of nomegestrol/estradiol: Study Protocol Version 4.0

20 JUN 2019

3 Responsible Parties

PRINCIPAL INVESTIGATOR:	[name] ZEG – Berlin Center for Epidemiology and Health Research [name] [name] Germany Email:	
STUDY CONDUCT:	ZEG – Berlin Center for Epidemiology and Health Research [name] [name] Germany	
Project Manager:	ZEG – Berlin Center for Epidemiology and Health Research [name] [name] Germany Email:	
FUNDER:	Merck Sharp & Dohme Corp. (hereafter referred to as the FUNDER) [name] [name] [name], U.S.A.	
FUNDER CONTACT INFORMATION 1	Merck & Co Inc [name] [name] United States Telephone - Office: Fax No.:	

PASS – Safety of nomegestrol/estradiol: Study Protocol Version 4.0

4 Abstract

Title

Prospective controlled cohort study on the safety of a monophasic oral contraceptive containing nomegestrol acetate (2.5mg) and 17β -estradiol (1.5mg)

Study protocol version of 05 February 2014

Author: [name], PhD Principal Investigator [name] [name] Germany

Rationale and background

NOMAC-E2 is a novel monophasic oral contraceptive containing a fixed dose of nomegestrol acetate (2.5mg) and 17 β -estradiol (1.5mg) being taken for 24 days followed by 4 days of placebo. The estrogen component is identical to the endogenous human 17 β -estradiol. It is unknown whether this regimen has an impact on the cardio-vascular risk associated with the use of hormonal contraceptives. It is also unclear whether the regimen has an impact on depressive disorders, hepatobiliary disorders, inflammatory bowel disease, body weight and acne.

Research question and objectives

The primary objective of the study is to characterize and compare the risks of the use of NOMAC-E2 with levonorgestrel-containing combined oral contraceptives $(COC_{LNG})^1$, in a study population that is representative for the actual users of the individual preparations. This includes an estimate of the absolute risk of rare serious adverse outcomes. The main clinical outcomes of interest for follow-up are venous

¹ cf. Section 9.2.1

PASS – Safety of nomegestrol/estradiol: Study Protocol Version 4.0 20 JUN 2019

thromboembolism, specifically deep venous thrombosis of the lower extremities and pulmonary embolism.

Study design

Multinational, controlled, prospective, active surveillance study that follows two cohorts. The cohorts consist of new users (starters² and restarters³) of two different groups of hormonal contraceptives: NOMAC-E2 and COC_{LNG}. The study will use a non-interference⁴ approach to provide standardized, comprehensive, reliable information on these treatments in a routine clinical practice setting. A 'non-interference' approach is used to provide standardized, comprehensive, reliable information under routine medical conditions. Study participants will be enrolled via an international network of 2,000 – 3,000 COC prescribing health care professionals. Study participants will be followed up for one to two years. All outcomes of interest will be captured by direct contacts between the investigator team and the study participants. Reported outcomes of interest will be validated via attending physicians and relevant source documents. The classification of outcomes of interest into 'confirmed' and 'not confirmed' will be verified by blinded independent adjudication.

Population

Approximately 101,000 study participants (50,500 NOMAC-E2 and 50,500 COC_{LNG} users) will be recruited via a network of 2000 – 3000 COC-prescribing health care professionals (e.g. gynecologists and general practitioners) in Australia, 9 European countries (Austria, France, Germany, Hungary, Italy, Poland, Russia, Spain and Sweden) and 2 Latin American countries (Colombia and Mexico). All starters and restarters (see above) of NOMAC-E2 or COC_{LNG} who are willing to participate in the study are eligible for enrollment into the study⁵.

Variables

Primary statistical variable: VTE hazard ratio for NOMAC-E2 vs. COC_{LNG} adjusted for age, BMI, duration of current use and family history of VTE. Results are based on patient-reported VTE that will be validated via the attending physicians and medical records. Other variables include arterial thromboembolism, depressive disorders, hepatobiliary disorders, inflammatory bowel disease, body weight and acne.

⁴ I.e., 1) all new users of NOMAC-E2 or COC_{LNG} are eligible for enrollment if they give their informed consent; and 2) recruitment of study participants should not influence the physician's prescribing, diagnostic, or therapeutic decisions.

² First ever user of a COC

³ User who restarts hormonal contraceptive use with a COC (same COC as before or new COC) after an intake break of at least two months.

PASS – Safety of nomegestrol/estradiol: Study Protocol Version 4.0 20 JUN 2019

Data sources

This is a field study. Exposure to hormonal contraceptives, concomitant medication, primary and secondary outcomes, potential confounding factors and potential effect modifiers will be documented by the study participants as well as the recruiting and attending physicians in the questionnaires, and additional documentation sheets, if needed.

Study size

The study is sufficiently powered to show non-inferiority of NOMAC-E2 compared to COC_{LNG} assuming that the true VTE risk among NOMAC-E2 users is not higher than among COC_{LNG} users. For this purpose, a total of 101,000 women (50,500 NOMAC-E2 and 50,500 COC_{LNG} users) will be followed up for approximately 150,000 womanyears (WY). The power calculations are based on the following parameters: 1) α of 0.05; 2) power (1- β) of 0.80 and 3) non-inferiority limit on hazard ratio of 1.5.

Data analysis

The final analyses will include both an "as treated" (AT) and an intention-to-treat (ITT) analysis using Cox regression models. The safety conclusions of the study, however, will be based on the AT analyses because the ITT approach potentially dilutes differences between treatments. The appropriate confounding variables will be built into the statistical models. Crude as well as adjusted hazard ratios (HRs) will be calculated. The null hypothesis to be tested is: $HR_{VTE} \ge 1.5$ (i.e., the VTE hazard ratio for NOMAC-E2 vs. COC_{LNG} is higher than or equal to 1.5). The alternative hypothesis is: $HR_{VTE} < 1.5$.

Milestones

Milestone	Planned date ⁶	
Start of data collection	March 2014	
End of recruitment	September 2019	
Last regular follow-up	September 2020	
End of data collection ⁷	December 2020	
Interim report 1	October 31, 2015	
Interim report 2	October 31, 2016 Actual Date (May 23, 2016)	
Interim report 3	December 2018	
Interim report 4	February 2020	

⁶ cf. Section 9.9 ("Limitations of the research methods"), last paragraph

⁷ includes 3 months of loss to follow-up activities after the last regular follow-up

PASS – Safety of nomegestrol/estradiol: Study Protocol Version 4.0	20 JUN 2019

Registration in the EU PAS register	March 2014	
Final report of study results	April 2021	

PASS – Safety of nomegestrol/estradiol: Study Protocol Version 4.0 20 JUN 2019

5 Amendments and updates

		-		
Number	Date	Section of Study Protocol	Amendments and updates	Reason
1 (v3.0)	20-FEB-2019	PASS Information	EU PAS Register number added	Number assigned following registration
			Medicinal product is only Zoely not IOA	Marketing authorisation was withdrawn for IOA in 2014
			Product reference updated to exclude IOA	Marketing authorization was withdrawn for IOA in 2014
			Marketing authorization holder for Zoely changed from Theramex to TEVA to a different Theramex	Change of MAH and reflection of shared funding between MSD and Theramex
			Delete MSD as MAH	Theramex is MAH for Zoely product
			Country(ies) of study: Sweden, Colombia and Mexico added	Expansion of recruitment to additional countries
			MAH contact person updated	Personnel change at MAH
		Section 2: List of Abbreviations	Addition of PQC	Acronym added to list due to expansion
		Section 3: Responsible parties	Funder contact information updated	Personnel change at MAH
			Safety Monitoring and Advisory Council members and experts updated	Departure and addition of members/experts

PASS – Safety	of nomegestrol/estradiol:	Study Protocol Version 4.0	20 JUN 2019
	or nornogood on ood daton.		20 0011 2010

		Section 4: Abstract	Addition of Sweden, Colombia and Mexico	Expansion of recruitment to additional countries
			Modification of milestones	Timelines modified to reflect study prolongation as agreed with EMA
		Section 6: Milestones	Modification of milestones	Timelines modified to reflect study prolongation as agreed with EMA
		Section 9.1: Study Design	Addition of Sweden, Colombia and Mexico	Expansion of recruitment to additional countries
		Section 9.2.2: Selection of study population	Text added to clarify expansion to Latin America.	Expansion of recruitment to additional countries
		Section 9.10: Other aspects	Correction of typos	Typos identified
		Section 11: Management and reporting of adverse events/adverse reactions	Text modified to omit Theramex	Funding of study shared between MSD and Theramex
		Section 11.1.2: Product Quality Complaint Reporting	Addition of section	To include reporting of product quality complaints for compliance with standards
		Section 11.1.3: Special Situations Reporting	Addition of section	To include special situations reporting for compliance with safety standards
1 (v.4.0)	20-JUN-2019	PASS Information	MAH contact person updated	Personnel change

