9.2.2 Selection of Study Population

Approximately 50,500 NOMAC-E2 users and 50,500 users of COC_{LNG} will be recruited by participating physicians, including adolescents. The proportion of adolescents is expected to be in the range between 10% and 15%. Overall, 101,000 study participants are needed in order to provide approximately 150,000 woman-years (WY) (cf. Section 9.5), assuming a drop-out rate of approximately 0.7% per month for both continents. Approximately 90% of subjects will be recruited in Europe and the other 10% in Australia. Subsequent to these original assumptions, the study was expanded to Latin American countries (Colombia and Mexico).

Recruitment of study participants will be conducted via existing networks of COCprescribing health care professionals (e.g. gynecologists and general practitioners) who have participated in similar cohort studies in the past. Physicians should recruit NOMAC-E2 and COC_{LNG} users in an approximate 1 to 1 ratio. It is expected that this ratio reflects approximately the ratio of starter and restarter prescriptions of NOMAC-E2 and COC_{LNG} under routine clinical conditions. For every NOMAC-E2 user recruited, the physician should recruit the next new COC_{LNG} user (starter or restarter) who is willing to participate in the study.

Subjects will be considered for enrollment in this study after the participating physician has determined that NOMAC-E2 or COC_{LNG} use is appropriate. There will be no specific medical inclusion/exclusion criteria and no age restrictions (to fulfill the pediatric investigation plan (PIP) requirement in the EU). However, women who 1) have been pregnant within 3 months before treatment initiation or 2) have a history of cancer/chemotherapy or an increased genetic risk for VTE at baseline will be excluded from the analysis of VTE. All women who are eligible are to be asked by their physician if they are willing to participate. As this is a non-interventional study, the possibility to participate in the study should not be discussed with the study participant before both

PASS – Safety of nomegestrol/estradiol: Study Protocol Version 4.0 20 JUN 2019

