9.3.2 Secondary Endpoints

For several other clinical outcomes an association to COC use has been discussed. For some outcomes a causal relationship has to be assumed (e.g., COC use and myocardial infarction in women with a combination of risk factors - in particular smoking, advanced age and high blood pressure) for other outcomes the existing evidence is weak (e.g. prolonged time to conception after stop of COC use). The selection of following secondary endpoints will be investigated in this study (cf. Section 8):

- All VTE
- Arterial Thromboembolism (ATE)
- 'Idiopathic' VTE (VTE cases with acute risk factors such as pregnancy, delivery, trauma, immobilization, long-haul travel, surgery, chemotherapy excluded)
- Depressive Disorders
- Cholelithiasis
- Inflammatory Bowel Disease (IBD)
- Fertility
- Drug Utilization Pattern and Baseline Risk for primary and secondary clinical outcomes in particular cardiovascular outcomes
- Pregnancy outcomes
- Weight change
- General hepatobiliary disorders
- Acne

Most of these secondary endpoints were successfully investigated in the EURAS study [1;2;3] and/or similar studies.

The secondary outcome of depressive disorders is included as an important identified risk, cholelithiasis, and inflammatory bowel disease as important potential risks, and safety in women during pregnancy as missing information in the NOMAC-E2 EU Risk Management Plan. The MAH included these outcomes in the study to further characterize the risk profile for NOMAC-E2.

Weight change:

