Incidence rates, incidence rate ratios (HRs), excess risks, as well as crude and adjusted hazard ratios will be calculated. The appropriate confounding variables will be built into the model. Based on the expectation of a small absolute number of serious outcomes of interest the number of confounding variables will be limited to wellestablished risk factors for these outcomes (e.g., age, BMI, duration of current use, and VTE history). Different modeling approaches will be used for the final multivariable model. The primary analysis model will be an *a-priori* expert model that is content driven and includes well-established prognostic factors. Additional sensitivity analysis models will be constructed to capture the influence of selected confounding factors and possible bias due to missing data. The final decision on the confounding variables will be made by the Safety Monitoring and Advisory Council before the first interim analysis of follow-up data. In addition, alternative analysis will be performed with other potential baseline risks to check the appropriateness of this decision. Similar analyses will be performed for all VTE (cf. Section 8) and arterial thromboembolism (e.g., acute myocardial infarction and stroke), the other secondary variables and other serious adverse events.

The null hypothesis to be tested is: $HR_{VTE} \ge 1.5$ (i.e., the VTE hazard ratio for NOMAC-E2 vs. COC_{LNG} is higher than or equal to 1.5). The alternative hypothesis is: $HR_{VTE} < 1.5$.

In the case of VTE it is conceivable that the proportional hazard assumption that effect parameters multiply hazard does not hold. Therefore, time-dependent factors will be included in the Cox model. The appropriateness of the model will be checked by comparing results of this analysis with results of an alternative analysis which stratifies by time of exposure. This stratification addresses also the potential problem of effect modification by current duration of use.

Real-life field studies frequently face the situation of missing data. The multiple reasons include superficial reading of the questions, misunderstanding of the questionnaire or simply unwillingness to give certain information. The questionnaires of this study have a clear layout and most questions have been tested in several former studies in large populations. The amount of missing information will be minimized by contacting participating women several times. If the missing information

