In contrast, it will be impossible to exclude diagnostic bias. Clinical symptoms of VTE cover the spectrum from a complete absence or unspecific, slight symptoms to dramatic, acute, life-threatening symptoms [17;18;19]. A high awareness of potential cardiovascular risks of combined oral contraceptive use may lead to more diagnostic procedures and, therefore, to more detected VTE. It is conceivable that this potential bias lead to an overestimate of the relative risk of a new product (such as NOMAC-E2) cohorts compared to the LNG-cohort. Therefore, diagnostic bias should not result in an underestimate of the VTE risk carried by NOMAC-E2.

Unlike in many other observational studies on hormonal contraceptives, a strength of the study will be the availability of information on many important prognostic factors for the outcomes of interest. Nevertheless, we acknowledge that due to the non-interventional character of the study, information on specific gene mutations will only be available for VTE cases but not for the vast majority of study participants who will not experience a VTE. This limitation will be mitigated through information on family history of VTE which has a higher predictive value for VTE compared to gene mutations [20].

This study combines several methodological strengths that are substantial for the validity of the results: i) prospective, comparative cohort design; ii) availability of important confounder information (e.g., BMI and family history of VTE); iii) validation of outcomes of interest and the exposure of the relevant cases; iv) comprehensive follow-up procedure and very low loss to follow-up to minimize underreporting; v) independent, blinded adjudication of VTE cases; vi) relevant statistical analyses (e.g., stratified analyses by user status and exposure period; comparison of isochronous, new user cohorts; sensitivity analyses on the impact of the adjudication process, outcome definition, and prognostic factor/covariate selection); vii) study population representative for oral contraceptive users under routine clinical conditions; viii) generalisability of results as COC use in this study reflects routine clinical use and

PASS – Safety of nomegestrol/estradiol: Study Protocol Version 4.0 20 JUN 2019

study participation is not limited by medical inclusion and exclusion criteria; ix) supervision by an independent Safety Monitoring and Advisory Council, and scientific independence from the study funder.

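### The exclusion of three groups from the VTE analysis is not limited to the hazard ratio, so the absolute VTE risk promised in the primary objective could describe a lower-risk subset of the enrolled users

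*Protocol*

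**What the plan says.** - **Objective (Abstract; Section 8).** The study is to characterize and compare risks in a study population "representative for the actual users of the individual preparations. This includes an estimate of the absolute risk of rare serious adverse outcomes". The text that follows names VTE (leg DVT and pulmonary embolism) as the main outcome, so an absolute VTE risk is part of the primary objective.
- **Enrolment (Section 9.2.2).** "There will be no specific medical inclusion/exclusion criteria and no age restrictions".
- **Exclusion from analysis (Section 9.2.2).** The next sentence lists women who "have been pregnant within 3 months before treatment initiation", and women who "have a history of cancer/chemotherapy or an increased genetic risk for VTE at baseline will be excluded from the analysis of VTE". Nothing there restricts the exclusion to the hazard ratio.
- **Measures (Section 9.7).** "Incidence rates, incidence rate ratios (HRs), excess risks, as well as crude and adjusted hazard ratios will be calculated".
- **Generalisability (Section 9.9).** The results are said to generalise partly because "study participation is not limited by medical inclusion and exclusion criteria".

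**The concern.** Taking these women out is a reasonable way to control confounding in a hazard ratio. An absolute risk has a different target. The excluded women are actual users, and they are enrolled and followed. By the protocol's own account most of the excluded characteristics raise VTE risk. A rate computed without these women therefore answers a narrower question than the one in the objective, and it errs on the favourable side for a safety outcome.

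The absolute VTE rate per product is a figure that prescribers and regulators are likely to quote. If it comes from the restricted set but is read as the risk in actual users, the objective is not met as written. The protocol plans no VTE rate in all enrolled women, and it does not say that the absolute-risk part of the objective applies only to the restricted set.

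**Working it through.** **Plan's own figure.** Section 9.5 asks for 150 VTE cases (one-sided α 0.05, power 0.80, limit 1.5, two equal cohorts). Schoenfeld's formula gives 4(1.645 + 0.842)²/(ln 1.5)² = 150.4, rounded up to 151. Power at 150 events is 79.9%. Also 10.0/10,000 WY × 150,000 WY = 150. The study-size figure reproduces and is not in dispute.

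**Direction.** Section 9.3.2 defines its idiopathic VTE endpoint as "VTE cases with acute risk factors such as pregnancy, delivery, trauma, immobilization, long-haul travel, surgery, chemotherapy excluded", so pregnancy, delivery and chemotherapy count as VTE risk factors. Section 9.7 mentions cancer diagnosis together with other acute VTE risk factors as a possible reason for censoring. Increased genetic risk for VTE is higher risk by definition. RR above 1 is therefore the reading that fits the protocol.

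**Formula.** Let r be the VTE rate in the retained women, p the share of enrolled woman-years in the excluded groups, and RR the VTE rate ratio of excluded to retained women.

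- Rate in all enrolled women = (1 − p)r + p·RR·r = r[1 + p(RR − 1)]
- Understatement by the restricted rate = 1 − 1/[1 + p(RR − 1)]

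The documents give neither p nor RR. The ranges below are assumptions. The enrolled-population rate is set at 10.0 per 10,000 WY for illustration.

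| p | RR = 2 | RR = 3 | RR = 5 | RR = 10 |
|---|---|---|---|---|
| 1% | 9.90 (−1.0%) | 9.80 (−2.0%) | 9.62 (−3.8%) | 9.17 (−8.3%) |
| 3% | 9.71 (−2.9%) | 9.43 (−5.7%) | 8.93 (−10.7%) | 7.87 (−21.3%) |
| 5% | 9.52 (−4.8%) | 9.09 (−9.1%) | 8.33 (−16.7%) | 6.90 (−31.0%) |

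Cells show the restricted rate per 10,000 WY and its difference from the enrolled rate. Worked example for p = 3%, RR = 5: 1 + 0.03 × 4 = 1.12; 10/1.12 = 8.93; 1 − 1/1.12 = 10.7%.

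**Events involved.** With 150,000/2 = 75,000 WY per cohort, the same example keeps 72,750 WY × 8.93/10,000 ≈ 65 of 75 expected events, so about 10 fall in the excluded women.

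**Sampling error.** The exact Poisson 95% CI for 75 events in 75,000 WY is 7.9 to 12.5 per 10,000 WY, that is, 21% below to 25% above the estimate. Most cells of the table lie inside this interval. Unlike sampling error, the shift runs in one direction and does not shrink with more woman-years.

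**Excess risk.** If p and RR are equal in both cohorts, the rate difference shrinks by the same factor. If p differs between cohorts, the difference can move either way.

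**The case against.** *The exclusion may be meant for the comparison only.* Section 9.7 defines the primary analysis by the hazard ratio's upper confidence limit, and Section 9.3.1 bases inference on that ratio. This stands in part. A reader might infer that the reported rate will certainly be too low, but the text does not settle whether the rule reaches the incidence rates, so the conclusion is conditional.

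*Denominators of descriptive tables belong in the SAP, which is not shown.* A SAP could add an unrestricted rate, and nothing forbids one. However, the protocol states a rule in general terms that conflicts with its own stated objective. That sentence needs correcting whatever the SAP contains.

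*Section 9.9 is literally true.* It speaks of participation, and participation is indeed unrestricted. The statement is therefore not false. It just does not carry over to a VTE rate from a restricted set.

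*Nothing is hidden.* A reader might infer that events in the excluded women disappear. Section 11.1 says all reported adverse events will appear in the final report, and the exclusion is openly stated. What is missing is a rate that includes these women.

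*The size is assumed.* Correct. The 31% cell needs p = 5% and RR = 10 together. A constant RR over up to 24 months is also generous for a group defined by pregnancy in the 3 months before treatment. Section 9.9 says gene mutations will be unknown for most participants, so few women may be excludable on genetic grounds. On the other hand, restarters need only a two-month intake break, so the cohorts can include women restarting after a pregnancy.

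**Conclusion.** The mismatch is real in conditional form. The objective promises an absolute risk for actual users. The exclusion in Section 9.2.2 is not limited to the comparison. If it is applied to the rates and excess risks of Section 9.7, the rates describe a lower-risk subset and understate the rate in enrolled users for any RR above 1.

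The size cannot be fixed from the document. It is about 2% at p = 1%, RR = 3 and about 11% at p = 3%, RR = 5, both assumed, and it may be small against sampling error. A reader might take this as a flaw in the main test. It is not: the exclusion is defensible for the hazard ratio, and neither the 1.5 limit nor the non-inferiority conclusion depends on this point.

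**What to change.** 1. In Section 9.2.2, state that the three groups are excluded from the comparative (hazard ratio) analysis of VTE.
2. In Section 9.7, add as-treated VTE incidence rates with 95% CI per cohort in all enrolled women, without these exclusions and without censoring at acute VTE risk factors. Lifting the exclusions alone would not be enough, because Section 9.7 foresees such censoring and it would again narrow the population described.
3. Show the restricted rate beside it, with the events and woman-years of the excluded women, and state which population each rate describes.

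The cost is a few sentences and one table. Sections 9.2.4 and 9.2.5 already provide for follow-up of all consenting women and validation of their events, so no new data are needed. The downside is a somewhat less favourable absolute rate that includes VTEs partly due to other causes, which the side-by-side display makes visible. The hazard ratio analysis and its limit stay as they are.
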